# 9.2 Serious Adverse Events (SAE) or Adverse Events (AE) felt to be related to 11C-methionine (IND #104987)

Participants will be carefully monitored and adverse events collected using the Common Terminology Criteria for Adverse Events version 4.0 (CTCAE) during active participation of the C-methionine PET scan. Active participation is defined as: from time of injection through one hour post injection of C-methionine. Vital signs (BP, RR, HR) will be assessed prior to receiving the

St. Jude Children's Research Hospital IRB NUMBER: Pro00004349

IRB Approval date:

Rev. 3.2 dated: 1/19/2023 Protocol document date: 1/19/2023 IRB NUMBER: Pro00004349

oval date: IRB APPROVAL DATE: 02/01/2023

injection and at the end of the MET PET scan. Participants will be watched continuously via an in-room camera during the scan.

### **REPORTING REQUIREMENTS:**

Office of Human Subjects' Protection (OHSP): The non-serious adverse events occurring during active participation will be reported to the OHSP in the continuing review reports. In addition to the continuing review reports to the Institutional Review Board, known as the Office of Human Subjects' Protection (OHSP), the principal investigator is responsible for the expeditious reporting of all serious, unexpected adverse events (AEs) involving research participants that occur during active participation. All adverse events occurring outside of active participation (injection to one hour post injection) will follow reporting rules set in Section 9.1.

Serious Adverse Events (SAEs) occurring during active participation that are unexpected-fatal or unexpected-life threatening are to be reported to the OHSP immediately, but every effort will be made to assure it is no later than 48 hours of notification of the event to the principal investigator or designees. All other unexpected (non-fatal or non-life threatening) SAEs occurring during active participation will be reported as soon as possible but within 10 working days of notification of the event. All other SAEs occurring outside of active participation will be reported according to the reporting rules in 9.1.

The SAE of expected death for all on study participants will be reported to the OHSP as soon as possible but no later than approximately 3 working days upon notification of event to the principal investigator or designees. Expected, life threatening SAEs noted during active participation will be reported to the OHSP as soon as possible but no later than 10 working days of notification of the event to the principal investigator or designees. All other SAEs (expected and non-life threatening) and captured AEs occurring during active participation will be reported to the IRB in the continuing review reports.

The term "life threatening" refers to any adverse experience that places the research participant, in the view of the investigator, at immediate risk of death from the reaction, as it occurred, not an event that hypothetically might have caused death if it occurred in a more severe form.

U.S. Food and Drug Administration (FDA): The study will be conducted under IND authorization. Any unexpected fatal or unexpected life-threatening event judged by the principal investigator to possibly be due to the investigational agent/radiopharmaceutical, will be reported to the FDA by telephone or fax as soon as possible but no later than 7 calendar days after notification of the event and followed by a written safety report as complete as possible within 8 additional calendar days (i.e., full report 15 calendar days total after notification of event).

IRB NUMBER: Pro00004349
IRB APPROVAL DATE: 02/01/2023

Unexpected, non-fatal and non-life-threatening SAEs, which occur in on-study, participants during the time period of active participation that are considered due to or possibly due to the injection of the radiopharmaceutical agent, will be reported to the FDA by written safety report as soon as possible but no later than 15 calendar days of the notification of the occurrence of the event. Expected SAEs, and unexpected fatal SAEs considered by the principal investigator to be unrelated to the study, will be reported to the FDA in the Annual Review Report along with non-serious AEs. All FDA correspondence and reporting will be conducted through the St. Jude Regulatory Affairs Office.

Copies of all correspondence to the St. Jude IRB, including SAE reports, are provided to the St. Jude Regulatory Affairs Office. All FDA related correspondence and reporting will be conducted through the Regulatory Affairs Office.

Continuing review reports of protocol progress and summaries of adverse events will be filed with the St. Jude OHSP, St. Jude Clinical Protocol Scientific Review and Monitoring Committee (CPSRMC), and FDA at least annually.

# 9.3 Recording Adverse Events and Serious Adverse Events

Adverse events (AEs) will be evaluated and documented by the clinical staff and investigators and graded using the scoring system according to the NCI Common Toxicity Criteria v4.0. Only the radiotherapy-related adverse events will be collected and scored. Adverse events will be reported per institutional policy. Both serious and unexpected adverse events (Grade 3-5) will be reported through the St. Jude TRACKS (Total Research and Knowledge System) system. Toxicity grading will be determined by the PI, radiation oncologist or neurosurgeon utilizing the pertinent patient history, physical exam and imaging studies. These events will be reported expeditiously to the St. Jude IRB within the timeframes as described above. Cumulative summary of Grade 3-5 events will be reported as part of the progress reports to IRB at the time of continuing review. Specific data entry instructions for AEs and other protocol-related data will be documented in protocol-specific data entry guidelines that have been developed and maintained by study team and clinical research informatics. CRAs are responsible for reviewing documentation related to AEs and entering directly into CRIS protocolspecific database.

## 9.4 Process for Reporting Adverse Events from and to Collaborative Sites

Adverse events occurring in patients enrolled by collaborating sites will also be reviewed by the PI and discussed in study team meetings. SAE reports from collaborating sites for AEs that are serious, unexpected, and at least possibly related to protocol treatment or interventions will be reported to the site's IRB per the site's local reporting and timeline requirements and to [name] at St. Jude within the reporting requirements.

St. Jude Children's Research Hospital IRB NUMBER: Pro00004349

IRB APPROVAL DATE: 02/01/2023

The PI will determine if the event needs to be reported expeditiously to all participating sites, considering the following criteria:

- Is the AE serious, unexpected, and related or possibly related to participation in the research?
- Is the AE expected, but occurring at a significantly higher frequency or severity than expected?
- Is this an AE that is unexpected (regardless of severity that may alter the IRB's analysis of the risk versus potential benefit of the research and, as a result, warrant consideration of substantive changes in the research protocol or informed consent process/document?

If the event does not require expeditious reporting to all sites, it will be included in the annual continuing review.

The PI will report all SAEs reported by collaborating sites to the St. Jude IRB using the "Reportable Event" in St. Jude TRACKS application per the timelines outlined in section 9.1.1 The PI will indicate if all sites should be notified to report to their IRBs, and if the protocol and/or consent should be amended (consent will be amended if event is information that should be communicated to currently enrolled subjects). Generally, only events that warrant an amendment to the protocol and/or consent will be reported expeditiously to all sites. However, any event may be reported expeditiously to all sites at the discretion of the PI.

# 9.4.1 Reporting Timelines:

For Collaborating Sites: Serious AND unexpected AND related events are to be reported to the St. Jude PI ([name] [name], DO, PhD) within five (5) working days of event awareness via fax or email. Unexpected deaths must be reported to the St. Jude PI via phone call or email within 24 hours of the event. A written report using the St. Jude "External Unanticipated Problem/Adverse Event Report" form available from the collaborative sites website must follow.

## 9.5 Radiation Safety Committee

Initial approval is not required.

#### 10.0 DATA COLLECTION, STUDY MONITORING, AND CONFIDENTIALITY

### 10.1 Data Collection

St. Jude Children's Research Hospital IRB NUMBER: Pro00004349 IRB APPROVAL DATE: 02/01/2023

IRB Approval date:

10.1.1 Electronic case report forms (eCRFs) will be completed by the SJCRH Radiation Oncology CRAs. Data will be entered into a secure database (CRIS) developed and maintained by St. Jude Clinical Research Informatics.

### 10.1.2 Data Collection Instructions for Collaborative Sites

Collaborating sites will collect data using e-CRFs via remote electronic data entry using the CRIS database. Protocol-specific data and adverse events will be recorded by the collaborating sites' clinical research associates ideally within 2 weeks of completion.

## 10.2 Study Monitoring

# High Risk 3 (HR-3) – Phase II or Phase III Therapeutic Studies with an IND or IDE

The Eligibility Coordinators will verify 100% of the informed consent documentation on all participants and verify 100% of St. Jude participants' eligibility status within 10 working days of the completion of enrollment.

The study team will meet at appropriate intervals to review case histories or quality summaries on participants.

The Clinical Research Monitor will assess protocol and regulatory compliance as well as the accuracy and completeness of all data points for the first 2 participants then 15% of study enrollees every 6 months. Accrual will be tracked continuously for studies that have strata. All SAE reports will be monitored for type, grade, attribution, duration, timeliness and appropriateness on all study participants *semi-annually*.

The monitor will also verify 100% of all data points on the first 2 participants and on 15% of cases thereafter. Protocol compliance monitoring will include participant status, eligibility, the informed consent process, demographics, staging, study objectives, subgroup assignment, treatments, evaluations, responses, participant protocol status, off-study, and off-therapy criteria. The Monitor will generate a formal report which is shared with the Principal Investigator (PI), study team and the Internal Monitoring Committee (IMC).

Monitoring may be conducted more frequently if deemed necessary by the CPDMO or the IMC.

Continuing reviews by the IRB and CT-SRC will occur at least annually. In addition, SAE reports in TRACKS are reviewed in a timely manner by the IRB/OHSP.

IRB APPROVAL DATE: 02/01/2023

St. Jude collaborating study sites will be monitored on-site by a representative of St. Jude at intervals specified in the Data and Safety Monitoring Plan. International collaborators will be monitored according to the study-specific monitoring plan.

#### 10.3 **Confidentiality**

Source documents from the study, which identify the study participant, will be kept confidential in a secured area and a password-protected database.

#### 11.0 STATISTICAL CONSIDERATIONS

The primary objective of this protocol is to prospectively estimate the PFS and OS distributions of children and young adults after a second course of irradiation and to demonstrate that many of these patients may be safely salvaged, if additional surgery and radiation therapy are administered. PFS and OS distributions will be measured from the initiation of re-irradiation. The historical data discussed below are retrospective and without correlative neuropsychological and quality of life information; thus, the data are not sufficiently convincing for most investigators.

To conduct this trial, we expect that a high percentage of patients will have received chemotherapy post progression and prior to registering on this trial. The primary objective will be assessed without regard to whether patients did or did not receive prior chemotherapy. However, the potential association of primary outcome with specific chemotherapy given prior to re-irradiation will be explored (exploratory objective 1.3.4).

### **Historical Data and Analyses**

These analyses should be interpreted as exploratory and p-values are to be interpreted descriptively and are not adjusted for multiple comparisons. Patients with ependymoma who experience initial failure may be characterized based on their pattern of failure type (POF1 = local failure, POF2 = distant or POF3 = combined). We analyzed 50 patients previously retreated between 2000 and 2011 according to their retreatment strategy. Possible retreatment strategies include focal retreatment, which was used only for patients with local failures (RT2focal), and craniospinal irradiation with focal irradiation of the metastatic site(s) and primary site when indicated (RT2CSI). RT2CSI was used for all patients with combined or distant failure and selected patients with local only failure

> St. Jude Children's Research Hospital IRB NUMBER: Pro00004349

[figure not shown]
IRB Approval date: IRB APPROVAL DATE: 02/01/2023

Table 11.0 Pattern of Failure and Treatment Strategy for Historical Cohort

Retreatment Group	Initial Pattern of Failure	Retreatment Strategy	N
A	$POF_1 = local$	$RT_{2focal}$ = focal irradiation	22
В	$POF_1 = local$	$RT_{2CSI} = craniospinal irradiation$	7
C	POF 2 = distant	RT 2CSI	16
D	$POF_3 = local + distant$	RT 2CSI	5
Total			50

The following figure and table provide Kaplan-Meier estimates of the distributions of Progression-Free Survival and Overall Survival for the 50 patients in the historical cohort. PFS and OS are measured from the date of re-irradiation (RT2) until failure (relapse, disease progression, second malignancy or death) or death, respectively. Patients who have not failed are censored at their last date of contact.

Figure 11.1 Progression-free and Overall Survival Historical Cohort

St. Jude Children's Research Hospital IRB NUMBER: Pro00004349 IRB APPROVAL DATE: 02/01/2023

Rev. 3.2 dated: 1/19/2023 Protocol document date: 1/19/2023

Table 11.1 PFS and OS for the Historical Cohort

[figure not shown]
	PFS						OS					
Years Since	Risk	Fail	Cens	Prob	SE	Years Since	Risk	Fail	Cens	Prob	SE	
Iniatiation of						Iniatiation of						
RT2						RT2						
0	50	0	0	1.000	0.000	0	50	0	0	1.000	0.000	
1	50	13	3	0.729	0.064	1	50	1	3	0.979	0.021	
2	34	5	2	0.621	0.072	2	46	9	5	0.778	0.064	
3	27	5	4	0.500	0.081	3	32	3	5	0.704	0.077	
4	18	3	3	0.402	0.086	4	24	3	3	0.607	0.087	
5	12	0	2	0.402	0.094	5	18	1	2	0.569	0.093	
6	10	0	1	0.402	0.098	6	15	2	2	0.493	0.101	
7	9	2	2	0.301	0.103	7	11	2	4	0.395	0.125	
8	5	0	1	0.301	0.113	8	5	0	1	0.395	0.137	
9	4	0	2	0.301	0.145	9	4	0	2	0.395	0.177	
11	2	0	2	0.301	0.252	11	2	0	2	0.395	0.307	

Descriptive statistics of the duration of initial disease control measured in years from the date of initial irradiation (RT1) until failure is shown in the next table.

	N	Mean	Std	Min	25 th %	Median	75 th %	Max
Duration of Initial Disease								
Control								
In Years	50	2.63	2.24	0.23	1.22	1.84	3.53	10.35

Kaplan-Meier estimates of the PFS after re-irradiation, by quartile of initial disease control, are shown in the following figure. Of the patients whose initial disease control was at least 3.53 years, only one has experienced disease progression after re-irradiation. The p-value for a log-rank comparison of the four groups is 0.0101.

Rev. 3.2 dated: 1/19/2023 Protocol document date: 1/19/2023

The following Cox models also suggest that duration of initial disease control is associated with duration of PFS and OS after re-irradiation.

Cox Model of PFS for Duration of Initial Disease Control									
Number of		Standar			95% Hazard				
Patients	Parameter	d		Hazard	Ratio Confidence				
(events)	Estimate	Error	Pr > ChiSq	Ratio	Limits				
50 (28)	-0.379	0.157	0.0159	0.685	0.503	0.932			

Cox Model of OS for Duration of Initial Disease Control									
					95% Hazard				
Number of	Parameter	Standard		Hazard	Ratio Confidence				
Patients (events)	Estimate	Error	Pr > ChiSq	Ratio	Limits				
50 (21)	-0.743	0.281	0.0081	0.476	0.275	0.825			

# Factors Associated with Outcome: Neuropathology at Initial Recurrence

[figure not shown]
The following table shows the distribution of neuropathology at initial recurrence, which was not available for 4 of the 50 patients.

[figure not shown]
Neuropathology at Recurrence							
Anaplastic Ependymoma (AEP)	26	52.0%					
Ependymoma (EP)	18	36.0%					
Focal Anaplastic Ependymoma (FAEP)	2	4.0%					
No Pathology	4	8.00%					

Below are Kaplan-Meier estimates of distributions of PFS and OS by recurrent histology. The Cox models following the figures suggest that patients with AEP at recurrence have a worse outcome as measured by PFS and OS.

Rev. 3.2 dated: 1/19/2023

Protocol document date: 1/19/2023

Cox Model of PFS for Recurrent Histology									
	Parameter   Standard   Hazard   95% Hazard Ratio								
	Estimate	Error	Pr > ChiSq	Ratio	Confidence Limits				
AEP vs. (FAEP+	1.13029	0.42714	0.0081	3.097	1.341 7.153				
EP)									

Cox Model of OS for Recurrent Histology									
Parameter Standard Hazard 95% Hazard Ratio									
	Estimate	Error	Pr > ChiSq	Ratio	Confidence Limits				
AEP vs.	1.55020	0.53783	0.0039	4.712	1.642	13.522			
(FAEP+EP)									

# Factors Associated with Outcome: Extent of Surgical Resection at Initial Recurrence

The following table shows the distribution of surgical resection with a gross total resection achieved in 68% of patients.

[figure not shown]
Extent of Surgical Resection or Metastasectomy								
Gross Total Resection (GTR)	34	68.0%						
Near Total Resection (NTR)	9	18.0%						
Sub Total Resection (STR)	7	14.0%						

[figure not shown]
Below are Kaplan-Meier estimates of distributions of PFS and OS by extent of surgical resection at initial recurrence. The Cox models following the figures suggest that patients for whom a gross total resection was achieved have better survival.

IRB Approval date:

Protocol document date: 1/19/2023

Rev. 3.2 dated: 1/19/2023

Cox Model of PFS for Extent of Surgical R	Resection
---	-----------

	Initi	Initial Disease Control in Years								
Neuropathology	≤ 1.22		1.22< - ≤		1.84< - ≤		3.53< - ≤			
at Recurrence			1.84		3.53		10.3	35	Totals	
	N	%	N	%	N	%	N	%	N	%
AEP	7	26.92	7	26.92	8	30.77	4	15.38	26	52.0
EP	4	22.22	2	11.11	4	22.22	8	44.44	18	36.0
FAEP	0	0	2	100.0	0	0	0	0	2	4.0
No Path	1	25.0	2	50.0	1	25.0	0	0	4	8.0
Totals	12	24.0	13	26.0	13	26.0	12	24.0	50	

		Parameter	Standard	Standard		95% Hazard Ratio	
		Estimate	Error	Pr > ChiSq	Ratio	Confide	ence Limits
GTR vs.	NTR +STR	-0.91550	0.42108	0.0297	0.400	0.175	0.914

Cox Model of OS for Extent of Surgical Resection											
	Parameter Standard Hazard 95% Hazard R										
	Estimate	Error	Pr > ChiSq	Ratio	Confidence Limits						
GTR vs.NTR+STR	-1.01384	0.47177	0.0316	0.363	0.144	0.915					

# Factors Associated with Outcome: Age at Time of Re-Irradiation

There is no evidence of any association between age at re-irradiation and PFS (p>0.85) or OS (p>0.94).

[figure not shown]
### Reasonable Prognostic Strata:

The association between duration of initial disease control and neuropathology at recurrence is shown in the following table.

Based on the above analyses of outcome, duration of initial disease control (IDC) longer than 3.53 years identifies a subgroup of approximately 24% of patients with an excellent outcome. Patients who experience shorter durations of initial disease control and have anaplastic ependymoma (AEP) at recurrence identifies a subgroup of approximately 44% of patients with a poor outcome. A third subgroup (Other) of approximately 32% of patients have FAEP or EP or no neuropathology at recurrence and initial disease control less than 3.53 years (<3.53). These three strata are proposed for monitoring PFS for the current trial against the historical data. PFS for the historical cohort by these three strata are shown in the following figure and table. A logrank comparison of the three groups results in a p-value of 0.0003.

IRB APPROVAL DATE: 02/01/2023

Rev. 3.2 dated: 1/19/2023 IR Protocol document date: 1/19/2023

[figure not shown]
>3.53						<=3.53 & AEP					Others				
Years	Risk	Fail	Cens	Prob	SE	Risk	Fail	Cens	Prob	SE	Risk	Fail	Cens	Prob	SE
Since															
Initiation															
of RT2															
0	12	0	0	1.000	0.000	22	0	0	1.000	0.000	16	0	0	1.000	0.000
1	12	0	2	1.000	0.000	22	11	1	0.476	0.104	16	2	0	0.875	0.080
2	10	1	1	0.900	0.095	10	2	1	0.381	0.106	14	2	0	0.750	0.104
3	8	0	3	0.900	0.116	7	4	0	0.163	0.075	12	1	1	0.688	0.116
4	5	0	2	0.900	0.142	3	0	0	0.163	0.075	10	3	1	0.458	0.127
5	3	0	0	0.900	0.142	3	0	1	0.163	0.086	6	0	1	0.458	0.138
6	3	0	0	0.900	0.142	2	0	1	0.163	0.106	5	0	0	0.458	0.138
7	3	0	2	0.900	0.201	1	0	0	0.163	0.106	5	2	0	0.275	0.117
8	1	0	0	0.900	0.201	1	0	0	0.163	0.106	3	0	1	0.275	0.135
9	1	0	0	0.900	0.201	1	0	1	0.163	0.149	2	0	1	0.275	0.166
11	1	0	1	0.900	0.285		·				1	0	1	0.275	0.234

# Factors Associated with Outcome: Initial Pattern of Failure and Retreatment Volume

These data are presented to provide evidence for the proposed retreatment volume based on site of tumor recurrence.

IRB APPROVAL DATE: 02/01/2023

Rev. 3.2 dated: 1/19/2023 Protocol document date: 1/19/2023

[figure not shown]

Log-rank test: p-value=0.2416

Rev. 3.2 dated: 1/19/2023

Protocol document date: 1/19/2023

	Log-rank test: p-value=0.2416														
POF1 & 1	RT2foc	al				POF2	2 & R7	T2CSI			POF3 & RT2CSI				
Years	Risk	Fail	Cens	Prob	SE	Risk	Fail	Cens	Prob	SE	Risk	Fail	Cens	Prob	SE
Since															
Initiation															
of RT2															
0	22	0	0	1.000	0.000	16	0	0	1.000	0.000	5	0	0	1.000	0.000
1	22	5	2	0.762	0.093	16	2	0	0.875	0.080	5	3	1	0.250	0.153
2	15	2	1	0.660	0.107	14	1	1	0.812	0.098	1	0	0	0.250	0.153
3	12	1	2	0.605	0.120	12	3	2	0.587	0.133	1	0	0	0.250	0.153
4	9	2	2	0.432	0.133	7	1	0	0.503	0.134	1	0	0	0.250	0.153
5	5	0	1	0.432	0.146	6	0	0	0.503	0.134	1	0	1	0.250	0.217
6	4	0	0	0.432	0.146	6	0	1	0.503	0.145					
7	4	1	1	0.324	0.154	5	1	1	0.377	0.149					
8	2	0	0	0.324	0.154	3	0	1	0.377	0.172					
9	2	0	0	0.324	0.154	2	0	2	0.377	0.298					
11	2	0	2	0.324	0.267										

[figure not shown]
Log-rank test: p-value=0.0242

POF1 & RT2focal							2 & R'	T2CSI			POF3 & RT2CSI				
Years	Risk	Fail	Cens	Prob	SE	Risk	Fail	Cens	Prob	SE	Risk	Fail	Cens	Prob	SE
Since															
Iniatiation															
of RT2															
0	22	0	0	1.000	0.000	16	0	0	1.000	0.000	5	0	0	1.000	0.000
1	22	1	2	0.950	0.048	16	0	0	1.000	0.000	5	0	1	1.000	0.000
2	19	2	3	0.841	0.087	16	2	1	0.875	0.083	4	3	0	0.250	0.153
3	14	1	2	0.781	0.106	13	1	3	0.802	0.113	1	0	0	0.250	0.153
4	11	3	2	0.533	0.138	9	0	0	0.802	0.113	1	0	0	0.250	0.153
5	6	0	1	0.533	0.149	9	0	0	0.802	0.113	1	0	1	0.250	0.217
6	5	0	0	0.533	0.149	9	2	1	0.624	0.145					
7	5	1	2	0.426	0.186	6	1	2	0.499	0.177					
8	2	0	0	0.426	0.186	3	0	1	0.499	0.204					
9	2	0	0	0.426	0.186	2	0	2	0.499	0.353					
11	2	0	2	0.426	0.323										

#### 11.1 **Statistical Analysis of Primary Objective 1.1**

The primary objective is to estimate the distributions of PFS and OS post reirradiation at initial failure for patients with ependymoma. In addition, we will monitor PFS as compared with the retrospective historical data discussed in section 11.0 to ensure that the current approach is not inferior to the retrospective historical experience.

Based on the work of Korn and Freidlin (2006) [297] we will estimate the sample size required to monitor that the prospective results are not inferior to the retrospective results, as if a prospective randomized trial were to be conducted. The historical PFS data were used to estimate the hazard rate during the first 4 years of 0.233 and for the hazard rate for the period greater than 4 years of 0.056. The following figure shows that a piece-wise exponential distribution with these two hazard rates is an outstanding fit to the historical PFS distribution.

The calculations for the monitoring design assume piece-wise exponential distributions. The design will have 80% power to detect an unacceptable decrease in the 3-year PFS rate from 50% to 35% ( $\alpha$ =0.10: one-sided test). East© (version 5) was used to calculate that with one interim analysis and approximately 64% of patients assigned to the new treatment, a total of 140 patients would need to be

IRB Approval date: IRB APPROVAL DATE: 02/01/2023 randomized over 9 years of accrual. Thus, we will need to accrue 90 patients to our new regimen over approximately 9 years. The final analyses will be conducted 2 years after initiation of irradiation for the last patient.

The one interim analysis, based on the work by Xiong et al, [298] will be conducted when 50% of the expected number of failures (67) for the 90 patients to be treated prospectively (assuming the alternative hypothesis) has been observed (~34 patients have failed). The planned interim analysis will occur at approximately 68% of the expected total "transformed information time," assuming the alternative hypothesis. Accrual will be suspended until all available information has been considered, if the observed nominal p-value is  $\leq 0.0582$ . At the final analysis, one would conclude that the prospective results are inferior to the retrospective results if the p-value is  $\leq 0.10$ . The log-rank comparisons will be stratified by three strata define above and the power should be retained [299]. With this design the actual significance level is 0.1089; the power is 0.7915 and the maximum probability of an interim decision being discordant with a decision that would be made by a final analysis is 0.05 (5%).

While the expected accrual to this trial is considerably greater than our historical experience, we expect that accruing 12 patients per year is realistic. Our current case review for re-irradiation includes approximately two chart review consultations per month. Patients treated to date include those previously irradiated in department or from our region. Based on institutional policy, patients cannot be accepted for treatment at St. Jude in the absence of a clinical protocol. Thus when this trial opens, we will begin to actively recruit patients for the trial. Furthermore, we have offers from a number of centers to collaborate in this effort. If accrual is not meeting expectations by the end of year 2, we will contact these centers to participate.

At the time of amendment #2, the study had been open for 4 years and we accured 53 patients. The accrual rate was approximately 10 patients/year and less than the 15 patients per year target (initial). We extended the accrual time by 3 years to reach the accrual goal and added a collaborative site.

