#### 3.3 Recruitment

The statistical design of this trial requires that 90 eligible patients be enrolled over a 9 year period. Accounting for ineligible patients, which are expected to be at most 10%, the total number of patients to be accrued to this study may be 99. We expect to enroll about 12 patients per year for approximately 9 years. The study will enroll patients with ependymoma and progressive disease. There is no exclusion to enrollment based on the time interval between initial tumor progression and enrollment. In the event that the accrual of patients is slower than expected, we will consider collaborating with other centers that specialize in the treatment of ependymoma. Patients with a prior history of radiosurgery may be excluded from protocol enrollment if the principal investigator or his designee determines that the risk of injury associated with fractionated retreatment is excessive.

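### The inputs stated in Section 11.1 give about 73–77% power for the as-if-randomised comparison, not 80%, and the power of the stratified test is asserted without a calculation

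*Combined protocol and SAP*

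**What the plan says.** Section 11.1 makes estimation of PFS and OS the primary objective and adds a check that PFS is not inferior to the retrospective experience. The check is sized as if the two groups had been randomised: "The design will have 80% power to detect an unacceptable decrease in the 3-year PFS rate from 50% to 35" per cent, one-sided alpha 0.10. PFS is taken as piecewise exponential, with hazards of 0.233 up to year 4 and 0.056 afterwards. The total is 140 patients, about 64% on the new regimen (90/140 = 0.643), accrued over 9 years. On timing: "The final analyses will be conducted 2 years after initiation of irradiation for the last patient". Section 3.3 repeats the sample size: "The statistical design of this trial requires that 90 eligible patients be enrolled over a 9 year period".

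One interim analysis is triggered at "50% of the expected number of failures (67) for the 90 patients", about 34 failures, at roughly 68% of the information on the plan's transformed scale. The interim boundary is p ≤ 0.0582 and the final boundary p ≤ 0.10.

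On the test itself: "The log-rank comparisons will be stratified by three strata define above and the power should be retained". The strata come from Section 11.0, Reasonable Prognostic Strata: "These three strata are proposed for monitoring PFS for the current trial against the historical data". Section 11.1 then reports: "With this design the actual significance level is 0.1089; the power is 0.7915". On accrual it adds, as of amendment 2: "We extended the accrual time by 3 years to reach the accrual goal".

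**The concern.** The 80% is the stated statistical basis for 90 patients as a guard against a regimen worse than past practice. A final result that does not cross p ≤ 0.10 will be read as reassurance, and the strength of that reassurance is the power. If power is 73–77%, the chance of missing a true fall from 50% to 35% is 23–27% rather than 20%.

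Two further figures looked doubtful: the 0.7915, which should follow from the same inputs, and the 67 expected failures, which should follow from 9 years of accrual plus 2 years of follow-up. Separately, the test to be used is stratified and has a fixed historical comparator, so the as-if-randomised figure does not describe it directly.

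**Working it through.** **Inputs (Section 11.1).** Hazards 0.233 then 0.056; 50 comparator and 90 new patients; p = 90/140, so p(1−p) = 0.2296; one-sided alpha 0.10 (z = 1.2816); 80% power (z = 0.8416). Assumptions: uniform accrual, proportional hazards throughout, no loss to follow-up (11.1 gives no rate).

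**Hazard ratio.** From the two rates: ln 0.35/ln 0.50 = 1.515 (log 0.4151). From the fitted control hazard: (−ln 0.35/3)/0.233 = 1.502 (log 0.4067).

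**Can 80% be reproduced?** Nearly, with one constant hazard: about 113 failures and power 0.798 (HR 1.515) or 0.786 (HR 1.502). That is not the piecewise model the section states.

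**Failures needed:** (1.2816 + 0.8416)²/(log HR² × 0.2296).
- HR 1.515: 4.508/(0.1723 × 0.2296) = 113.9
- HR 1.502: 4.508/(0.1654 × 0.2296) = 118.7

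**Failures expected.** Follow-up at the final analysis is uniform on 2 to 11 years. The mean failure probability is (1/9)∫₂¹¹[1 − S(u)]du.
- Comparator: 0.635 × 50 = 31.8
- New regimen: 0.778 × 90 = 70.05 (69.8 at HR 1.502)
- Total: 101.8 (101.6 at HR 1.502)

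**Power.**

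| Method | HR 1.515 | HR 1.502 |
|---|---|---|
| Schoenfeld: Φ(log HR × √(D × 0.2296) − 1.2816) | 0.766 | 0.753 |
| Inverse variance: Φ(log HR/√(1/d₀ + 1/d₁) − 1.2816) | 0.745 | 0.732 |
| Simulated log-rank, 20,000 trials | 0.749 | 0.730 |

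For example, 0.4151 × √(101.8 × 0.2296) − 1.2816 = 0.725, and Φ(0.725) = 0.766.

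**Decrease detectable with 80% power.** Solving each formula for 0.80 gives HR 1.549 (Schoenfeld) and 1.573 (inverse variance). Then 0.50^1.549 = 0.342 and 0.50^1.573 = 0.336: a fall from 50% to about 34%.

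**The 0.7915.** I used information time 0.68, the interim boundary p ≤ 0.0582 and the final boundary p ≤ 0.10. I added a lower interim boundary at p ≈ 0.294, chosen so that type I error equals 0.1089. A fixed-sample power of 0.80 then returns 0.791. Starting from 0.732–0.766, the same rule returns about 0.72–0.76. Without a lower boundary, type I error is 0.117 and 0.80 becomes 0.814, which matches neither stated figure.

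**The 67 failures.** Expected failures among the 90, with 2 years of follow-up: 6-year accrual 66.97; 7.5-year 68.6; 9-year 70.05. Section 11.1 mentions an initial target of 15 patients a year, and 90/15 = 6 years. Half of 66.97 is 33.5; half of 70.05 is 35.0. Under uniform 9-year accrual, the 34th failure is expected at year 5.99 and the 35th at year 6.11.

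**The stratified test (illustration only).** Historical 3-year PFS is 0.500 overall (Table 11.1) but 0.900, 0.163 and 0.688 in strata of 12, 22 and 16 patients. If HR 1.515 applies within strata, simulated power is roughly 0.69–0.76. If the overall rate falls from 50% to 35% and the stratum differences are as large as observed, the within-stratum HR is about 2.0 and power about 0.96. With those differences shrunk to a quarter on the log-hazard scale, power is about 0.76–0.79. These runs assume stratum hazards and historical follow-up that the plan does not give.

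**The case against.** The as-if-randomised trial is only a sizing device, and the comparison is a monitoring check added to an estimation objective. The gap is small: the effect detectable with 80% power moves by about one percentage point of 3-year PFS. That stands, and it limits the weight of the point.

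The software inputs are not in the documents, so this may be an error of description. A constant hazard nearly restores 80%. So does 5-year follow-up (Schoenfeld 0.780–0.793), and the Protocol Summary does give five years after the last enrolment as the primary outcome time frame. But Section 11.1 states piecewise hazards and a 2-year final analysis beside the 80%, so something there needs changing either way. Accrual was also not uniform. Placing the reported 53 patients in the first 4 years and 37 in the next 5 gives 71.5 new failures, close to 70.

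A reader might infer more than the documents support:
- That the plan gives no power for the stratified test. It prints 0.7915 directly after the stratification sentence. What is missing is the derivation.
- That the stratified test is underpowered. The illustrations fall on both sides of 80%, depending on which effect is meant.
- That 0.7915 was certainly carried over from the nominal 80%. The match needs a lower interim boundary that the plan does not state, and I chose it to fit 0.1089. It is suggestive only.
- That the interim trigger should move to 35. The timing difference is negligible, and the trigger is pre-specified.

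**Conclusion.** The stated 80% does not follow from the stated inputs. About 102 failures are expected against 114–119 needed, giving 73–77% power. This rests on uniform accrual, proportional hazards and no loss to follow-up; any loss would lower it further. Applying the effect in years 0–4 only gives 0.749–0.762 by Schoenfeld, inside the same range.

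The 0.7915 probably inherits the 80%, but that is not proven. The 67 failures fit 6 + 2 years better than 9 + 2. That is consistent with a figure left over from before the accrual extension, though this too is inference. For the stratified test against the historical cohort, the documents do not settle whether power is above or below 80%. They give 28 historical PFS failures at design, and Section 11.11 provides for periodic updates of that cohort, but no failure count is tied to the power. Nor do they say whether 50% to 35% is an overall or a within-stratum effect. The point is worth correcting but moderate.

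**What to change.** 1. Check the East inputs against the piecewise hazards and the 2-year follow-up. Unless that check changes the stated inputs, restate the as-if-randomised power as about 73–77%, or quote the decrease detectable with 80% power (50% to about 34%).
2. Update the 0.7915 that depends on it, and state any lower interim boundary used.
3. State the accrual and follow-up behind the 67 expected failures. Leave the trigger of about 34 where it is.
4. Show the calculation behind the claim that stratification retains power: the historical failure count assumed, and whether 50% to 35% is overall or within stratum. Since the strata were chosen from the same 50 patients, give a range for the differences between them.

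The cost is recalculation and wording, with no extra patients, visits or delay. The drawbacks are a slightly less favourable headline power and, for the stratified test, a range instead of a single figure.
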